5.1 Inclusion criteria

5.1.1 Solid malignant tumors (except primary central nervous system malignant tumors)

Patients with solid tumors are eligible to be included in the study only if all of the following inclusion criteria and none of the exclusion criteria apply:

Informed consent

1. Provision of signed and dated, written informed consent and any locally required authorization (eg, Health Insurance Portability and Accountability Act in the US, European Union [EU] Data Privacy Directive in the EU), from each patient or patient's legally acceptable representative, parent(s) or legal guardian in accordance with regional laws or regulations and the patient's assent, when applicable, before any study-specific activity, including screening evaluation, is performed. For patients who reach the age of legal consent during the clinical study, notification may be required and a new consent form may need to be signed by the patient.

The ICF process is described in Appendix A 3.

Age

2. Age from birth to <18 years of age at the time of screening.

Type of patient and disease characteristics

3. Patients must have a histopathologic confirmation of malignancy. Patients must have progressed or are refractory to standard therapies (see Appendix A 10), and for whom no standard of care treatments exist.
4. If a patient has a diagnostic CCI [REDACTED], provision of this sample is mandatory for study entry CCI [REDACTED] and is preferred in formalin-fixed paraffin-embedded blocks (FFPE). If no tissue is available or the CCI [REDACTED] Tumor lesions used for CCI [REDACTED] should not be the same lesions used as RECIST 1.1 or International Neuroblastoma Response Criteria (INRC)

target lesions (TLs), unless there are no other lesions suitable for biopsy (reassessment after biopsy may be required).

5. Lansky play performance scale ≥ 50 (Appendix J) for patients ≥ 1 and < 16 years of age and Karnofsky performance status score ≥ 50 (Appendix I) for patients ≥ 16 years of age (patients < 1 year of age are exempt from this criterion).
6. At least 1 lesion, not previously irradiated, that can be accurately evaluated or measured by RECIST 1.1 (Appendix E), INRC for NB (Appendix F). Tumor radiological assessments must be performed within 21 days prior to first dose. Lesions in a previously irradiated field can be used as measurable disease, provided that there has been demonstrated progression in the lesion

Or

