2 ANALYSIS SETS

2.1 Definition of analysis sets

Details of the analysis sets are presented in [Table 3](#) and [Table 4](#).

Table 3 Analysis sets

Analysis Set	Definition	Phase derived for
Full analysis set (FAS)	The FAS will include all patients who were assigned to treatment and received at least 1 dose of study treatment. The FAS (or subset of the FAS specified below) will be used for all efficacy analyses.	Dose-finding and Dose-expansion
Evaluable for response analysis set	
The subset of patients in the FAS who had
 
 • measurable disease (per RECIST 1.1) at baseline 
 ○ and had at least one follow-up scan measuring all required target lesions ○ and have been followed for at least 3 cycles (to allow for a confirmatory scan at 4 weeks after the first assessment scan) 
OR
 
 • measurable disease (per RECIST 1.1) at baseline 
 ○ and progressed or died in the absence of a follow-up scan. 	Dose-expansion
Safety analysis set (SAS)	The SAS will consist of all patients who received any amount of study treatment. Safety data will be summarized using the SAS according to the treatment received.	Dose-finding and Dose-expansion

Table 3 Analysis sets

Analysis Set	Definition	Phase derived for
Dose-limiting toxicity (DLT) evaluable analysis set	The DLT evaluable analysis set is a subset of the SAS for the dose-finding phase of the study. It includes all patients enrolled in the dose-finding phase of the study who receive the protocol-assigned treatment with durvalumab + tremelimumab and complete the safety follow-up through the DLT evaluation period (Cycle 1 + Cycle 2) or experience a DLT during the DLT evaluation period.	Dose-finding
PK analysis set	All patients who receive at least 1 dose of study treatment per the CSP for whom any post dose data are available and who do not violate or deviate from the CSP in ways that would significantly affect the PK analyses will be included in the PK analysis set. The population will be defined by the Study Physician, Pharmacokineticist, and Statistician prior to any analyses being performed.	Dose-finding and Dose-expansion
ADA analysis set	All patients who receive at least 1 dose of study treatment per the CSP for whom baseline, and any post dose data are available will be included in the ADA analysis set.	Dose-finding and Dose-expansion

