3.1 Prior treatment with immune-mediated therapy of any of the following

- Anti-PD-L1
- Anti-PD-1
- Anti- Programmed cell death ligand 2(PD-L2)
- Anti- Cytotoxic T-lymphocyte-associated antigen 4 (CTLA-4)
- Antibodies of chimeric antigen receptor T-cell therapy (CAR-T) or other cell therapies

3.2 Receive a live attenuated vaccine within 30 days prior to the first dose of study treatment

3.3 Receive an immunosuppressive medication within 14 days prior to the first dose of study excluding;

- Intranasal, inhaled, topical steroids, or local steroid injections (e.g. intra-articular injection).
- Systemic corticosteroids at physiologic doses as replacement therapy, not to exceed 10 mg/m²/day of prednisone or its equivalent.
- Steroids as premedication for hypersensitivity reactions (e.g. computed tomography (CT) scan premedication).

Dose-expansion phase

- Deviation 1: Patients who received a dose of study treatment other than the dose that was intended

1.1 Patient either did not receive any dose of planned study treatment or did not receive the correct dose of planned study treatment (i.e. less than 75% of the planned dose at the time of infusion) (as per Figure 1 in the CSP).

- Deviation 2: Patients who deviate from key entry criteria as per the CSP. These are inclusion criteria 2, 3, 6 and 8 and exclusion criteria 11:

- 2.1 Patient, older than 18 years, received study treatment (inclusion criteria 2).
- 2.2 Patient received study treatment without a histopathologic confirmation of a malignancy or/and have not progressed or were refractory to standard therapies or/and have not explored standard of care treatments before participation on this protocol. (inclusion criteria 3).
- 2.3 Selection of a previously radiated tumor as a target lesion and tumor did not show disease progression prior to study entry (inclusion criteria 6).
- 2.4 Inadequate organ and marrow function, defined as any of the following (inclusion criteria 8):
 - Hemoglobin < 9.0 g/dL
 - Absolute neutrophil count < $1.0 \times 10^9/L$
 - Platelet count < $75 \times 10^9/L$
 - Serum bilirubin > $1.5 \times$ the ULN

- Creatinine clearance ≤ 60 mL/min
 - Alanine transaminase (ALT) or aspartate transaminase (AST) $>3 \times$ upper limit of normal (ULN) (for patients without liver metastases)
 - ALT or AST $> 5 \times$ ULN (for patients with liver metastases)

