3.1.1.1 Target lesions (TLs) – site Investigator data

Measurable disease is defined as having at least one measurable lesion, not previously irradiated, which is ≥ 10 mm in the longest diameter (LD), (except lymph nodes which must have short axis ≥ 15 mm) with CT or magnetic resonance imaging (MRI) and which is suitable for accurate repeated measurements. A patient can have a maximum of 5 measurable lesions recorded at baseline with a maximum of 2 lesions per organ (representative of all lesions involved and suitable for accurate repeated measurement) and these are referred to as TLs. If more than one baseline scan is recorded, then measurements from the one that is closest and prior to first dose will be used to define the baseline sum of TLs. It may be the case that, on occasion, the largest lesion does not lend itself to reproducible measurement. In which circumstance the next largest lesion, which can be measured reproducibly, should be selected.

All other lesions (or sites of disease) not recorded as TL should be identified as NTLs at baseline. Measurements are not required for these lesions, but their status should be followed at subsequent visits.

Note: For patients who do not have measurable disease at entry (i.e. no TLs) but have non-measurable disease, evaluation of overall visit responses will be based on the overall NTL assessment and the absence/presence of new lesions (see Section 3.1.1.3 for further details). If a patient does not have measurable disease at baseline, then the TL visit response will be not applicable (NA).

Table 6 TL Visit Responses (RECIST 1.1)

Visit Response	Description
CR	Disappearance of all TLs. Any pathological lymph nodes selected as TLs must have a reduction in short axis to <10 mm.
PR	At least a 30% decrease in the sum of diameters of TLs, taking as reference the baseline sum of diameters as long as criteria for PD are not met.
SD	Neither sufficient decrease in sum of diameters to qualify for PR nor sufficient increase to qualify for PD.
PD	A $\geq 20\%$ increase in the sum of diameters of TLs and an absolute increase of $\geq 5\text{mm}$, taking as reference the smallest previous sum of diameters since treatment started including the baseline sum of diameters.
NE	Only relevant if any of the TLs were not assessed or NE or had a lesion intervention at this visit. Note: If the sum of diameters meets the progressive disease criteria, progressive disease overrides NE as a TL response.

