NA	No TLs are recorded at baseline.

CR Complete response; PD Progressive disease; PR Partial response; SD Stable disease; NA Not applicable; NE Not estimable.

Rounding of TL data

For calculation of PD and PR for TLs percentage changes from baseline and previous minimum should be rounded to one decimal place before assigning a TL response. For example, 19.95% should be rounded to 20.0% but 19.94% should be rounded to 19.9%.

Missing TL data

If all TL measurements are missing then the TL visit response is NE. Overall visit response will also be NE, unless there is a progression of non-TLs or new lesions, in which case the response will be PD.

Lymph nodes

For lymph nodes, if the size reduces to < 10 mm then these are considered non-pathological. However, a size will still be given, and this size should still be used to determine the TL visit response as normal. In the special case where all lymph nodes are < 10 mm and all other TLs

are 0mm then although the sum may be > 0 mm the calculation of TL response should be over-written as a CR.

TL visit responses subsequent to CR

A CR can only be followed by CR, PD or NE. If a CR has occurred, then the following rules at the subsequent visits must be applied:

- Step 1: If all lesions meet the CR criteria (i.e. 0mm or < 10 mm for lymph nodes) then response will be set to CR irrespective of whether the criteria for PD or TL is also met i.e. if a lymph node LD increases by 20% but remains < 10 mm.
- Step 2: If some lesion measurements are missing but all other lesions meet the CR criteria (i.e. 0mm or < 10 mm for lymph nodes) then response will be set to NE irrespective of whether, when referencing the sum of TL diameters, the criteria for PD are also met.
- Step 3: If not all lesions meet the CR criteria and the sum of lesions meets the criteria for PD then response will be set to PD.
- Step 4: If after steps 1 – 3 a response can still not be determined the response will be set to remain as CR.

TL too big to measure

If a TL becomes too big to measure this should be indicated in the database and a size ('x') above which it cannot be accurately measured should be recorded. If using a value of x in the calculation of TL response would not give an overall visit response of PD, then this will be flagged and reviewed by the study team blinded to treatment assignment. It is expected that a visit response of PD will remain in the vast majority of cases.

TL too small to measure

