If a TL becomes too small to measure, then this will be indicated as such on the eCRF and a value of 5mm will be entered into the database and used in TL calculations. However, a smaller value may be used if the radiologist has not indicated 'too small to measure' on the eCRF and has entered a smaller value that can be reliably measured. If a TL response of PD results, then this will be reviewed by the study team.

Irradiated lesions/lesion intervention

Previously irradiated lesions (i.e. lesion irradiated prior to entry into the study) should be recorded as NTLs and should not form part of the TL assessment.

Any TL (including lymph nodes), which has had intervention during the study (for example, irradiation / palliative surgery / embolization), should be handled in the following way and

once a lesion has had intervention then it should be treated as having intervention for the remainder of the study noting that an intervention will most likely shrink the size of tumors:

- Step 1: the diameters of the TLs (including the lesions that have had intervention) will be summed and the calculation will be performed in the usual manner. If the visit response is PD, this will remain as a valid response category.
- Step 2: If there was no evidence of progression after step 1, treat the lesion diameter (for those lesions with intervention) as missing and if $\leq 1/3$ of the TLs have missing measurements then scale up as described in the 'Scaling' section below. If the scaling results in a visit response of PD then the patient would be assigned a TL response of PD.
- Step 3: If, after both steps, PD has not been assigned, then, if appropriate (i.e. if $\leq 1/3$ of the TLs have missing measurements), the scaled sum of diameters calculated in step 2 should be used, and PR or SD then assigned as the visit response. Patients with intervention are evaluable for CR as long as all non-intervened lesions are 0 (or $<10\text{mm}$ for lymph nodes) and the lesions that have been subject to intervention have a value of 0 (or $<10\text{mm}$ for lymph nodes) recorded. If scaling up is not appropriate due to too few non-missing measurements, then the visit response will be set as NE.

At subsequent visits, the above steps will be repeated to determine the TL and overall visit response. When calculating the previous minimum, lesions with intervention should be treated as missing and scaled up (as per step 2 above).

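### SAP 3.1.1.1 leaves out the protocol's exception for irradiated lesions that have progressed, so measurable disease for the primary ORR set depends on which text is followed

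*SAP*

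**What the plan says.** **Protocol 5.1.1, criterion 6.** The general rule is "At least 1 lesion, not previously irradiated, that can be accurately evaluated or measured by RECIST 1.1". An exception follows: "Lesions in a previously irradiated field can be used as measurable disease, provided that there has been demonstrated progression in the lesion".

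**SAP 3.1.1.1.** The definition keeps the general rule only: "Measurable disease is defined as having at least one measurable lesion, not previously irradiated". Under the heading on irradiated lesions and lesion intervention, a previously irradiated "lesion irradiated prior to entry into the study) should be recorded as NTLs and should not form part of the TL assessment". Neither statement is qualified for progression.

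**SAP 2.2, dose-expansion deviation 2.3**, which cites criterion 6, lists as a deviation: "Selection of a previously radiated tumor as a target lesion and tumor did not show disease progression prior to study entry".

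**SAP 2.1, Table 3.** Both branches of the evaluable-for-response set require "measurable disease (per RECIST 1.1) at baseline". Table 4 makes this the set for the primary ORR, with the FAS as sensitivity analysis.

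**SAP Table 6.** The target-lesion (TL) response is NA when "No TLs are recorded at baseline".

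**SAP Section 5** applies the SAP's derivation rules to the DRC's stage 1 review. **SAP Section 6** lists the changes from the protocol; the handling of irradiated lesions is not among them.

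**The concern.** The protocol and the SAP give different answers to the same baseline question: can an irradiated lesion that has since progressed be a target lesion? The SAP also disagrees with itself. Limiting deviation 2.3 to lesions that had not progressed makes sense only if a progressed one is acceptable, and 3.1.1.1 does not allow that.

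Measurable disease is the entry condition for the primary ORR set, so the same baseline record can give two different lists of evaluable patients. The SARCOMA decisions rest on small counts (at least 2 responses in 11, then at least 5 in 26), where one patient can matter.

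**Working it through.** **1. What happens to a patient if 3.1.1.1 is applied as written**

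- *Case (a): every measurable lesion was irradiated and then progressed.* The patient is eligible under criterion 6. Under 3.1.1.1 all lesions are non-target and there is no measurable disease, so the patient is outside the evaluable-for-response set. With no TL recorded, the TL response is NA. The TL = NA rows of Table 8 give CR, SD, NE or no evidence of disease, and PD follows from non-target progression or a new lesion. No row gives PR. Shrinkage short of disappearance is Non-CR/Non-PD (Table 7) and therefore SD.
- *Case (b): the patient has both irradiated-then-progressed and unirradiated lesions.* Set membership is safe. But the two rules can select different target lesions and so different sums of diameters. The 30% decrease for PR and the 20% increase (with 5 mm) for PD are judged on those sums, so PR, SD or PD may differ.
- *If the site recorded the irradiated lesion as a TL.* The SAP's note on patients without measurable disease equates that state with having no TLs, and Table 6 says the same. Both point to deriving the visit response from the recorded TL, so PR is attainable. The remaining doubt is whether such a patient has measurable disease for Table 3.

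**2. The plan's own design**

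Inputs (Protocol 9.2, SAP 1.3): n1 = 11, stop if 1 or fewer respond; N = 26, reject if 5 or more respond; p0 = 0.10, p1 = 0.30.

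P(reject) = Σ(x=2..11) P(Bin(11,p) = x) × P(Bin(15,p) ≥ 5 − x)

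- p = 0.10: 0.0865, within the stated 0.1
- p = 0.30: 0.8516, meeting the stated 85%

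**3. How often the two readings would disagree in case (a)**

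Assumptions: exactly one such patient among the first 11, the same response probability for everyone, and enrolment that continues until 11 and then 26 evaluable patients are reached. Criterion 6 counts that patient (response X); 3.1.1.1 counts the next patient instead (response Y).

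Stage 1 differs only if the other 10 have exactly one response and X ≠ Y:

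P = P(Bin(10,p) = 1) × 2p(1 − p)

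- p = 0.10: 0.3874 × 0.18 = 0.0697
- p = 0.30: 0.1211 × 0.42 = 0.0508

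For the final decision, let S be the responses among the other 10, M those among patients 13 to 26, and Z the response of patient 27. Criterion 6 rejects H0 if S + X ≥ 2 and S + X + Y + M ≥ 5. SAP 3.1.1.1 rejects if S + Y ≥ 2 and S + Y + M + Z ≥ 5. Exact enumeration of disagreement gives:

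- p = 0.10: 0.0261
- p = 0.30: 0.0572

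All four probabilities split equally between the two directions.

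**4. FAS sensitivity analysis, if the case (a) patient has a PR that cannot be scored**

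The plan inflates evaluable numbers by about 1.2 (21 to 25, 36 to 43).

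- Full accrual: 26 × 1.2 = 31.2 dosed; 1/31 = 3.2 percentage points
- Stage 1 only: 11 × 1.2 = 13.2 dosed; 1/13 = 7.7 percentage points

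**The case against.** Table 3 asks for measurable disease per RECIST 1.1, and Table 5 of the SAP sends the reader to protocol Appendix E. If Appendix E carries the exception, the set definition may already include it. If it matches 3.1.1.1, the SAP has not departed from the protocol's response criteria, and the gap in Section 6 matters less. Section 6 also says the set definition was aligned with the DRC charter. Neither Appendix E nor the charter was available for this review. This stands as a reason to check both first. It does not remove the conflict between criterion 6, deviation 2.3 and the SAP's own definition.

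The protocol also admits patients with evaluable but not measurable disease, so some eligible patients fall outside the primary set by design. That is true, but criterion 6 expressly classes case (a) patients as measurable.

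The figures are conditional on an event of unknown frequency, and they model case (a) only. Continued enrolment is also partly inferred: replacement of non-evaluable patients is stated outright for dose-finding only. For expansion it follows from the evaluable-patient targets and the 20% allowance. Both limits stand.

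Two stronger readings are tempting and not supported. A reader might infer that the SAP would strip a recorded target lesion of its status and so block a PR. The note and Table 6 point the other way, and the SAP's intervention steps concern treatment of a lesion during the study. A reader might also infer that sites are handling these lesions differently. Nothing in the documents shows that.

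**Conclusion.** The conflict is in the text and should be resolved. SAP 3.1.1.1 contradicts criterion 6 and SAP deviation 2.3, and the difference is not declared. Applied as written, it removes case (a) patients from the primary ORR set and rules out PR for them in the FAS analysis when no TL is recorded. In case (b) it can change the sum of diameters. For a lesion already recorded as a TL, the doubt is confined to membership of the evaluable set.

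The frequency is not given, so no total effect can be stated. On the assumptions above, one case (a) patient among the first 11 gives disagreement at stage 1 with probability 7.0% (ORR 10%) or 5.1% (ORR 30%), and in the final decision with probability 2.6% or 5.7%.

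A reader might infer that the primary ORR is biased or the design's operating characteristics are damaged. The documents do not support that. With enrolment to the evaluable targets and a common response probability, the disagreements are symmetric, and type I error (8.7%) and power (85.2%) are the same under either rule.

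**What to change.** Check protocol Appendix E and the DRC charter, then settle on one rule.

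- **If criterion 6 governs:** in SAP 3.1.1.1, add to the measurable-disease definition *or previously irradiated with demonstrated progression in the lesion before study entry*. Limit the sentence that assigns irradiated lesions to the NTLs to those without such progression.
- **If the stricter rule is intended:** list it in SAP Section 6 as a change from the protocol, align deviation 2.3 with it, and state how an irradiated lesion already recorded as a TL is handled, including for the evaluable set.

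Apply the chosen rule before database lock to the baseline lesion records as collected. Do not re-select target lesions in knowledge of response.

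The cost is two SAP sentences, or a Section 6 entry, an edit to deviation 2.3 and a handling statement, plus a check of baseline lesion records. No new patient assessments are needed. The check needs prior irradiation and progression recorded for each lesion. The documents do not show that these are captured in the database, so source notes may have to be consulted for some patients.

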3.1.1.3 Overall visit response – site Investigator data

[Table 8](#) defines how the previously defined TL and NTL visit responses will be combined with new lesion information to give an overall visit response.

Table 8 Overall visit responses

TARGET	NON-TARGET	NEW LESIONS	OVERALL VISIT RESPONSE
CR	CR or NA	No (or NE)	CR
CR	Non-CR/Non-PD or NE	No (or NE)	PR
PR	Non-PD or NE or NA	No (or NE)	PR
SD	Non-PD or NE or NA	No (or NE)	SD
PD	Any	Any	PD
Any	PD	Any	PD
Any	Any	Yes	PD
NE	Non-PD or NE or NA	No (or NE)	NE
NA	CR	No (or NE)	CR
NA	Non-CR/Non-PD	No (or NE)	SD
NA	NE	No (or NE)	NE
NA	NA	No (or NE)	NED

CR Complete response; PD Progressive disease; PR Partial response; SD Stable disease; NA Not applicable; NE Not estimable; NED No evidence of disease.

